5.1. Imaging assessment of OA progression

Joint Space Narrowing (radiography): Measurement of joint space narrowing via radiographs is the current validated standard for quantifying the progression of OA in clinical studies⁶⁷, and is serving as the primary imaging outcome measure⁵⁴. Joint space width measurements are obtained from radiographs based on the semi-flexed metatarsophalangeal (MTP) view as originally described Buckland-Wright¹⁴. The

Subjective grading (radiography): The overall condition of the joint via radiographs will be graded using the system developed by Daniel et al ²⁶. Weightbearing A-P, lateral and tunnel radiographs of the knees are taken before surgery and at the final follow-up visit. A grade of 0 (normal) to 3 (severe) will be assigned to six different radiographic factors: osteophyte formation, subchondral sclerosis, femoral condyle flattening, subchondral cysts, ligament calcification, and joint space narrowing. Each factor will be subdivided within regions of the knee. For example, osteophytes will be graded according to size (0=no osteophyte; 1=1- to 3-mm; 2=4- to 6-mm, and 3=>6-mm) in eight different sites; the medial femoral and tibial condyles, the lateral tibial and femoral condyles, femoral notch, tibial spine, femoral aspect of the patellofemoral joint, and the patella. A total radiographic score of 83 is possible, which represents severe damage. A zero represents no damage. A radiologist ([name]), who is blinded to the subject number and the subject's group assignment, evaluates all of the films.

Table 4: The scanning sequences being utilized for the MRI examinations (3T). The protocol was designed to provide the data to perform cartilage thickness measurements and the WORM scores while limiting MRI time to 1 hour per visit.

Sequence	Outcome
Sagittal T1-weighted water-excitation (WE) three-dimensional (3D) fast low-angle shot (WE-3D FLASH): 20/7.6 [TR msec/ TE msec]; 12° [flip angle]; 160 mm [field of view, FOV]; 1.5 mm/0 [slice thickness/interslice gap]; 80 slices per slab; 130 hz/pixel [bandwidth, BW]; 512x512 [matrix]; right/left [phase encoding axis]; one average of two excitations. This sequence will cover all articular cartilage plates in the knee.	Volume; Thickness; WORM score
Coronal Intermediate-weighted turbo-spin echo (TSE): 3850/29; 7 [echo train length]; 140 mm; 3mm/0mm; 41 slices; 352 hz/pixel; 307x384; right/left; one average.	WORM score
Sagittal* T2*-weighted WE-3D double echo steady state (WE-3D DESS): 16.3/4.7; 25°; 140 mm; 0.7mm/0mm; 185 hz/pixel; 307x384; anterior/posterior; one average.	WORM score
Sagittal Intermediate-weighted TSE with fat-saturation: 3200/30; 5 ETL; 160 mm; 3mm/0mm; 248 hz/pixel; 313x448; superior/inferior; one average.	WORM score

From the sagittal T2-weighted WE-3D FLASH sequence, additional MR images will be reconstructed in both the transverse axial and coronal planes.

Cartilage Thickness (MRI): Magnetic resonance (MR) imaging of both knees will be performed on a 3T whole-body scanner (Siemens TIM Trio; Erlangen, Germany) using a commercially available circularly-polarized knee surface coil to measure temporal changes in cartilage thickness ^{11,12}. Scans were obtained at the time of recruitment and after 36 and 84 months of healing and will be taken at the 144- and 180-month follow-up visits. The cartilage thickness calculations will be based on the sagittal water-excitation T1-weighted 3D FLASH sequence (Table 4). A trained technologist, under the direction of the radiologist, will perform manual segmentations on all slices (1.5mm) for each knee using Mimics software ¹¹. MRI's will be segmented in pairs and blinded to sequence. Segmented slices will then be grouped to generate a 3-D mesh to represent the volumetric shape ^{11,12,65}. Once segmented, the cartilage structure will be registered between the multiple scans of the same subject taken at 0, 36, 60 and 84 months, the change in the shape of the cartilage will be characterized, and the shape and its change will be averaged and normalized across subjects. The segmented cartilage will be considered as unorganized point clouds, and intra-subject registration will be based on closest point algorithm ^{20-22,53,60}. This will enable alignment of the cartilage between time points (0, 36, 60 and 84 months) with a point-wise description of change. We will then focus our thickness measurements to the cartilage regions of the tibiofemoral joint with the greatest load bearing requirements. A cylinder will be fit to the bone-cartilage interface of the femoral cartilage of the reconstructed images. The notch marking the junction between the TF and patellofemoral joints on the lateral condyle is easy to identify on the sagittal MR view. A line will then be drawn from the notch (0°) to the center of the cylinder ¹². Each condyle of the TF joint will then be divided at 40°, 70°, 100°, and 130° from the notch point toward the posterior aspect of the condyles to create 6 patches of cartilage (3 medial, 3 lateral); the width of each patch will be 20% of the overall width of the femoral cartilage and centered about the midline of each condyle (Fig. 6). Two patches on the tibial cartilage (1 medial, 1 lateral) will also be defined by calculating the centroid of each compartment and the inertial axes of the medial compartment using MATLAB (The Mathworks, Inc., Natick, MA). The inertial axes will serve as a coordinate system, and the patch in each compartment will be defined as the area ±20% of the overall depth (A-P) and ±15% of the overall width (M-L) from the centroid ¹². The average thickness of each patch will be calculated by the closest point. The cartilage volume will be quantified for the

tibia and femur by the numerical integration of the number of voxels contained within the segmented regions for each bone³². The cartilage volumes will be normalized by the surface area of underlying bone from the Time 0 data set (pre-operative visit) in order to increase the construct validity of the measurement⁴⁷. Subjects will be labeled as having OA if they exhibit a cartilage volume loss exceeding 2.5% per year over the study period. This value was selected because patients without OA have been shown to have changes of 0.5% per year while those with OA lose approximately 4-6% per year⁴³. Although the changes in the cartilage volume for the femur will be assessed, the focus will be on the volume changes of the tibial condyles where OA is easiest to detect¹⁸, and most affected by ACL injury³⁶. **Note: Due to problems with artifact, this outcome measure was discontinued. The other imaging outcome measures were performed as originally planned.**

Whole Organ Magnetic Imaging Score (secondary MRI measure): The general status of the knee will be independently assessed by an expert musculoskeletal radiologist ([name]) and the PI using the semi-quantitative WORM score^{56,71,77}. The scoring utilizes four MR sequences (Table 5). The images are scored with respect to 14 independent features⁵⁶. Cartilage signal and morphology (8-point scale), subarticular bone marrow abnormality (4-point scale), subarticular cysts (4-point scale), subarticular bone attrition (4-point scale), and marginal osteophytes (8-point scale) will be evaluated in 15 regions (2 in the patella, 6 in the femur, 7 in the tibia). The regions are subdivided by distinct anatomical landmarks as described by Peterfy⁵⁶. In addition, the menisci (5-points), cruciate and collateral ligaments (2-points each), synovitis (4-points), loose bodies (4-points), and periarticular cysts (3-points) are scored. A total of 332 points per knee is possible. WORM scores are calculated for each feature in each compartment and for all features combined. The musculoskeletal radiologist assessing the WORM scores has the expertise in doing so for ACL injured patients^{28,73,74}.

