This study is designed to compare two common initial graft tension protocols for ACLR that influence joint contact mechanics. The first treatment group consists of patients whose grafts were tensioned to restore the normal anterior-posterior displacement of the tibia relative to the femur (“AP laxity”) at the time of surgery (i.e. AP laxity equal to that of the contralateral normal knee; the “low-tension” treatment). The second treatment group consists of patients whose grafts were tensioned to over-constrain the joint (i.e. AP laxity 2mm less than that of the contralateral knee; the “high-tension” treatment). In the last funding cycle, we have shown that the initial joint contact conditions between these two groups are significantly different in cadavers³⁹, and that the associated laxity differences in patients are different *in vivo*. The two treatment groups are being compared to a third matched control group. Fifty-four subjects were enrolled into each group. With this update, they will be followed 180 months after surgery. We are planning to follow these patients for a minimum of 15 years. Significant changes in cartilage integrity are expected within this long-term time frame in this patient population^{26,35,50}.

Radiographic assessment of joint space narrowing is the only validated indicator of structural change used to evaluate OA progression in clinical studies, and it will continue to be the primary outcome measure of cartilage damage⁶⁷. MR images of the articular cartilage and associated knee joint structures will provide secondary structural biomarkers for the early detection of OA³¹. MRI is being used to directly measure changes in cartilage thickness in the load bearing regions^{11,12}, while joint integrity will be assessed using the Whole Organ Magnetic Imaging Score (WORM score)⁵⁶. Using these imaging-based outcome measures, we will test the primary hypothesis:

- *Tibiofemoral joint space width (via radiography) and cartilage thickness (via MRI) in the reconstructed knees of the “high-tension” treatment group will be equal to that of the control group, while the joint space width and cartilage thickness in the “low-tension” treatment group will be significantly less than that of the control group 15 years after surgical reconstruction of the anterior cruciate ligament.*

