Surgical outcome will also be assessed via: 1) patient-oriented outcome scores^{59,76}, 2) AP laxity (an indicator of graft integrity^{6,44} and knee kinematics²³), 3) isokinetic strength (an indicator of dynamic knee function¹⁶), and 4) clinical outcome scores^{48,78}. Analysis of primary and secondary outcomes will enable us to determine the long-term effects of initial graft tension on cartilage status and knee joint function, and to evaluate the relationships between longitudinal changes that occur in tibiofemoral (TF) joint space (x-ray), cartilage thickness (MRI), general MRI scores (WORM score), knee laxity (KT-1000), strength (Biodex strength test, 1 legged hop test) and patient-oriented outcome scores (SF-36, Knee Osteoarthritis Outcome Score). In the past funding cycle, data were obtained from ACL-reconstructed patients pre-operatively, immediately post-operatively, and after 6, 12, 36, and 84 months of healing. From the control group data were obtained at the time of recruitment and at 12, 36, and 84 months. In this update, additional evaluations will be performed 144 and 180 months in the ACLR and control subjects, a time frame in which cartilage damage should become prevalent in the ACLR patient population. We intend to follow these patients for a minimum of 15 years.

RESEARCH DESIGN AND METHODS

1. Overview of Research Design

This investigation is designed as a prospective, randomized, double-blinded clinical study evaluating the effects of two different initial tension conditions applied to an ACL graft at the time of fixation on healing using biomechanical, clinical, and patient-oriented outcome measures. The primary outcome is evaluating the progression of OA via objective radiographic measurements of joint space narrowing. We are also assessing temporal changes in cartilage thickness, and the integrity of various knee joint structures using MRI. We will test the hypothesis that tibiofemoral (TF) joint space width (via radiography) and cartilage thickness (via MRI) in the reconstructed knees of the “high-tension” treatment group will be equal to that of the control group, while the joint space width and cartilage thickness in the “low-tension” treatment group will be significantly less than that of the control group 15 years after surgical reconstruction of the ACL. We intend to follow these patients for a minimum of 15 years.

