60 “matched” control subjects, who had no known history of knee injury or symptoms of arthritis, were recruited from the hospital campus, local colleges, and Providence community. They were selected to match the frequency of individuals by age (± 5 years), gender, race, and activity level (Tegner score ± 1 point). The subjects’ knees were evaluated by clinical exam at a screening visit. Subjects were not included in the control group if they have a side-to-side difference in AP laxity greater than or equal to 2-mm (KT-1000), a Tegner activity score less than 5⁶⁹, or if they meet any of the other exclusion criteria (Table 1). It was our intent to establish a control group that matched the characteristics of the population at risk to ACL injury.

3. Research Design

This study is designed as a prospective, randomized, double-blinded controlled trial comparing the outcome of two different initial tension conditions applied to the ACL graft at the time of surgery, and to determine the relationship between factors that may predict who will be risk for OA. The project statistician and the operating surgeon initially knew a patient’s assignment at the time of surgery, however, the

surgeon was not allowed to review the assignment once the surgery was completed, and the statistician was not allowed to review the assignments until after all the subjects were enrolled. The patient, the therapist performing the follow-up assessments, the AP laxity and isokinetic strength testing, the engineer performing the radiographic joint space width and cartilage thickness measurements, and the radiologist performing the WORM scoring will continue to be blinded from the subject's group assignment throughout the study. An intent-to-treat protocol is being utilized. All subjects randomized to each group are being followed, and all available data will be analyzed even if the graft fails, if the subject is unwilling to perform a particular follow-up test (missing data), or if a subject completely drops out of the study.

Table 1. Inclusion/exclusion criteria for patient enrollment.

Treatment Groups (Hi- and Lo-tension)	
Inclusion Criteria	Male or female subjects between the ages of 15 and 50 years with unilateral ACL injury.
	Candidates for ACLR using bone-PT-bone or four-stranded hamstring tendon autograft.
	A Tegner activity score ⁶⁹ ≥ 2 .
	Minor tears of the menisci that require minimal treatment (<1/3).

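### Cartilage thickness is recorded as discontinued yet remains in the 15-year hypothesis, and the primary joint space width model has no time level after 84 months

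*Combined protocol and SAP*

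**What the plan says.** The Specific Aims rank the imaging measures. Of radiographic joint space narrowing they say that "it will continue to be the primary outcome measure of cartilage damage", and they describe the MRI measures as secondary. They then write "Using these imaging-based outcome measures, we will test the primary hypothesis". That hypothesis covers joint space width and cartilage thickness together, comparing each tension group with control at 15 years. Section 1 (Overview of Research Design) repeats it: "We will test the hypothesis that tibiofemoral (TF) joint space width (via radiography) and cartilage thickness (via MRI".

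In section 5.1, the Cartilage Thickness (MRI) entry describes patch thickness, then cartilage volume, with a rule that labels a subject as having OA when volume loss exceeds 2.5% per year. It closes with the note "Due to problems with artifact, this outcome measure was discontinued" and adds that the remaining imaging measures went ahead as planned. Section 7 names only WORM scoring as the use of the extension scans.

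On visits, the Specific Aims say that "data were obtained from ACL-reconstructed patients pre-operatively, immediately post-operatively, and after 6, 12, 36, and 84 months of healing". Controls were seen at recruitment, 12, 36 and 84 months. Evaluations at 144 and 180 months are added for all groups.

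Section 8 contains three relevant models:
- **Primary:** a repeated-measures model for joint space width, with time levels baseline, 12, 36, 60 and 84 months.
- **Secondary:** repeated-measures models for knee kinematics, dynamic function, patient-reported and clinical outcomes, with group, limb and time for measures made on each limb.
- **Laxity-OA:** a random coefficient model in the experimental subjects, with joint space width and cartilage thickness as dependent measures.

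**The concern.** The update sets the hypothesis at 15 years, but the parts of the plan that would test it were not brought into line. A measure that section 5.1 records as discontinued is still half of the hypothesis as worded, and the primary model, read literally, leaves out the visits that the extension was set up to collect.

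Two decisions therefore remain open: what counts as a test of the hypothesis when one component is missing, and how the 12- and 15-year joint space width data enter the primary model. The note at the end of section 8 says that the 7-year results are published and that extension data are being collected. If these points are settled only at analysis, they will be settled by people who have seen earlier results and possibly the later data.

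**Working it through.** There is no disputed figure here, so most of the check sets the sections side by side.

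**1. Scope of the note.** Three things indicate that the whole entry (thickness and volume) was dropped: the note sits under the single heading Cartilage Thickness (MRI); it contrasts this measure with the other imaging measures; and section 7 gives WORM scoring as the only use of the extension scans. The note does not name thickness or volume, or the visits affected. The isokinetic note in section 5.4, by contrast, names the 12- and 15-year assessments.

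**2. What still depends on thickness.** The hypothesis has two components, joint space width and thickness. On this reading, 1 of 2 has no 15-year measurement. The laxity-OA model has the same two dependent measures; its joint space width analysis runs unchanged and its thickness analysis does not extend to 15 years.

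**3. Visits against the primary time factor.**

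| Month | Visit listed in Specific Aims | Level in primary model |
|---|---|---|
| 0 | yes | yes |
| 6 | ACLR only | no |
| 12, 36, 84 | yes | yes |
| 60 | no | yes |
| 144, 180 | yes (extension) | no |

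The immediate post-operative evaluation, also ACLR only, is not a level either. None of the 2 extension visits is a level, and 1 of the 5 levels (60 months) is not a listed visit. The last level leaves out 180 − 84 = 96 months, or 96/180 = 53% of the planned follow-up. The linear and quadratic time contrasts would likewise end at 84 months.

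Tables 2 and 3, which may give the schedule, are not in the text available for review, and the joint space width entry in section 5.1 is cut short there. The 60-month mismatch is therefore with the Specific Aims only.

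**4. Outcome sets.** Section 5 defines five: imaging, patient-oriented, knee kinematics, dynamic function and clinical. The secondary list in section 8 names the last four. Joint space width has the primary model; WORM, labelled a secondary MRI measure in section 5.1, is not named. It is scored per knee, so the existing group, limb and time model fits it.

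**5. Sample size.** Inputs from section 8: difference 0.25 mm, SD 0.35 mm, α = 0.05 (taken as two-sided), power 0.80, 35 per group.
- n per group = 2(1.960 + 0.842)² × 0.35² / 0.25² = 2 × 7.849 × 0.1225 / 0.0625 = 30.8, so 31 (32 with the t distribution).
- With 35 per group, t-test power is 0.838 and the detectable difference is 0.238 mm.
- With the unrounded mixture SD, √(0.20² + 0.5 × 0.5 × 0.6²) = 0.361 mm, n is 34, power is 0.816 and the detectable difference is 0.245 mm.

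The stated 35 is adequate for 0.25 mm over 84 months, and no thickness quantity enters the calculation.

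**The case against.** The strongest reply is that these are leftovers from an earlier funding cycle. Joint space width is plainly primary: the Specific Aims say so, section 5 makes the first test in each category the primary one, and the primary model and sample size use nothing else. The laxity-OA analysis on joint space width still runs. The per-limb rule already supplies a form for WORM. An analyst would probably add the later visits, which PROC MIXED can accommodate. Most of this stands, and it limits the point to alignment of the text. It does not remove the conflict: the hypothesis still names a measure recorded as discontinued, and the primary time levels are an explicit list that ends at 84 months.

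A second reply is that only volume was dropped. The sentences just before the note concern volume. The blinding text still names "the engineer performing the radiographic joint space width and cartilage thickness measurements", and the FLASH row of Table 4 still reads "Volume; Thickness; WORM score". This cannot be excluded, but it is weak: that sequence also serves WORM, and WORM needs the later scans in any case. Nor would it rescue the plan. Thickness would remain in the hypothesis without a group-versus-control comparison in section 8, because the laxity-OA model may consider tension group but uses experimental subjects only.

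A reader might also infer that the primary outcome is compromised, that the laxity-OA analysis is lost altogether, or that the extension MRI has no applicable model. The documents support none of these, for the reasons above.

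**Conclusion.** The point holds as an internal conflict that should be corrected before the 15-year analysis. If the note covers thickness, as its heading and context indicate, the thickness component of the hypothesis (1 of 2, and the lower-ranked one) and the thickness version of the laxity-OA analysis cannot be carried out at 15 years. Whatever the note covers, the primary model as written includes neither extension visit and has one level, 60 months, that the Specific Aims do not list. Imaging is missing from the secondary list, but this is an omitted category rather than a missing method.

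The conclusion rests on the most natural reading of the note, which the document does not state outright, and on a text without Tables 2 and 3.

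**What to change.** 1. State in the section 5.1 note that it covers thickness and volume, and which visits are affected. If thickness was in fact kept, say so and give it a group-versus-control comparison in section 8.
2. If thickness was dropped, restate the 15-year hypothesis in the Specific Aims and section 1 on radiographic joint space width only. Remove thickness from the laxity-OA model or limit it to visits with valid data, and mark the 2.5% per year volume rule as not in use.
3. Extend the time factor of the primary model to 144 and 180 months, and reconcile the 60-month level with the visits in the Specific Aims.
4. Add imaging to the secondary outcomes in section 8: WORM under the existing per-limb model, with the combined score named as the main score, labelled as specified after the 7-year results.

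The cost is wording only; the radiographs and MRI scans are already planned. The downsides are a narrower hypothesis if thickness was dropped, and a secondary MRI analysis specified late, which the label in item 4 makes plain.
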